### Selection of Subjects

Patient Selection: Patients undergoing tonsillectomy +/- adenoidectomy at Duke University Hospital and Duke Regional Hospital or a Duke Affiliated Ambulatory Surgical Center (including Davis Ambulatory Surgical Center) will be recruited for enrollment. Selection criteria are as follows:

Inclusion Criteria (IC): Children age >=3 and <18 yrs having elective tonsillectomy +/-adenoidectomy with signed, informed consent by parent or legal guardian. Post pubescent females are required to have a negative pregnancy test within 48 hours of surgery. Children >12 years must give assent.

Exclusion Criteria (EC): Patients with any of the following: 1. history of or known liver or kidney disease 2. Consistent daily opioid use for chronic pain (defined as ongoing pain >3 months) 3. severe sleep apnea (Sleep study with Apnea Hypopnea Index (AHI) > 10). 4. planned admission to the Pediatric Intensive Care Unit (PICU) following surgery 5. additional procedures under the same general anesthetic for which outpatient opioids would be prescribed.

Patients undergoing procedures such as PE tubes, nasal endoscopy, Auditory Brain Response tests, imaging studies do not have to be excluded.

#### Subject Recruitment and Compensation

Patients will be screened and properly identified by the principal investigator or member of the clinical research team assigned to the study through IRB-approved review of the surgical schedule. An IRB-approved phone call may be conducted to introduce the study or patients may be approached on the day of surgery allowing sufficient time for explanation, questions and answers. If interested, legal guardians may provide consent for the study via an IRB approved electronic Informed Consent Form (ICF) in advance or paper consent may be obtained on the day of surgery. For patients 12 years or older, patient assent for enrollment in the study will also be obtained.

Goal recruitment is 60 patients to complete the study. Subjects will be compensated a \$10 gift card (mailed) for the time and effort to complete 1-7d daily surveys and the phone call on day 30 following surgery.

#### **Study Interventions**

Study Intervention and Randomization: Subjects in each cohort will be randomized 2:1 methadone to short acting opioid using randomization tables generated by The Biostatistics Group within the Department of Anesthesia. Each subject is assigned the next number. To consider children in different age may have different pain tolerance, we will balance the treatment groups by age. That is, we will generate a set of blocked randomization numbers for three age groups, 3-6, 7-12, and 13-17 years old. Anesthesia providers receive a sealed envelope or email with Group (drug) assignment, group-specific instructions, and are advised on study procedures. To ensure full double-blinding, subjects, investigators, and study team members evaluating patients will be blinded to drug treatment. The rationale for 2:1 randomization is to achieve the same sample size for each group since we anticipate 2 methadone cohorts, thus final groups (methadone 0.1 mg/kg, methadone 0.15 mg/kg, controls) would each have 20 subjects.

As clarified above, the use of a short duration opioid in this specific study population (tonsillectomy 3-18 year olds) is a standard of care procedure. Methadone is standard of care in pediatric cardiac surgery, pediatric spine surgery and precuts excavatum surgery (3-18 year olds). Not counting the randomization, the dosing and administration of all 3 of these drugs (methadone, fentanyl, hydromorphone) are in line with standard of care practices for pediatric population of between 3 and less than 18 years and are routinely used both in and out of the operating room environment.

Regarding the clinical study of an investigational drug that would be IND exempt, the following ARE true for this study (see below):

- The investigation of a drug that is lawfully marketed in the US and the following 5 criteria are met:

the study is not designed to support approval of a new indication or change in labelling: No new indications sought

the study does not intend to support significant change in advertising of the product: No new advertising sought

the study does not significantly increase risks (or decrease the acceptability of risks) associated with the use of drug through route of administration, study population, dosage level, or anything else: No increase risks associated with the use of the drug, purposeful conservative dosage chosen for study with protective and specific dose escalation criteria the study is conduced in compliance with IRB and consent regulations: true, once IRB application amended and approved to the satisfaction of the IRB reviewers the study will not advertise or promote the use of the drug for the indication that it isn't approved for: No new indications or promotion of the drug sought.

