#### **Design & Procedures**

Study Design: Single center, randomized, double blind, parallel-group dose escalation investigation. All patients will receive standard monitoring for anesthesia and postoperative care. Surgical and anesthesia care (except for intraoperative opioid management) are not altered for study purposes. Subjects are randomized 2:1 to either long-duration (methadone) or short-duration opioid (fentanyl, hydromorphone). The use of any short acting opioid (ie: fentanyl, hydromorphone or both) is considered the control group and total dose, timing of administration, frequency of administration, and dose per administration of either/both short acting opioids will be administered at the discretion of the anesthesiologist as per standard of care practice. Because methadone analgesia for pediatric tonsillectomy has not previously been studied, this pilot study will use escalating dose groups to determine the optimal dose for this procedure. In order to achieve this, our trial design will include two periods. In the first period, we will randomly assign 20 patients to methadone 0.1 mg/kg and 10 patients to typical shortduration opioid (controls). An interim analysis will be conducted to determine if we should escalate to the higher dose of methadone. Methadone dose escalation to 0.15mg/kg age ideal body weight will occur if there is no difference in non-methadone PACU opioid use and no increased adverse events. If proceeding to the second period, we will recruit 20 patients for 0.15 mg/kg methadone and 10 patients as controls. Sample size for this pilot investigation was based on prior studies.

Defining an optimal dose of methadone is a crucial aim of this study, which will allow for future investigations, but is not a primary or secondary outcome. The dose finding nature of this study requires interim assessments after each methadone dose cohort. After the first 20 methadone subjects at 0.1mg/kg age ideal body weight, there will be a planned partial analysis of PACU opioid use. Methadone dose escalation to 0.15mg/kg age ideal body weight will occur if there is no difference in non-methadone PACU opioid use and no increased adverse events. Sample size for this pilot investigation was based on prior studies.

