Pre-operative, Intra-operative, Post-operative Care: Anesthesia and surgical care are not altered for this study except for randomization to the study drug. Oral or IV midazolam for anxiolysis may be given at standard dosing. Anesthetic induction via inhaled sevoflurane or intravenous agents are to be given at the anesthesiologist's discretion.

Patients in the short-duration opioid group receive short-duration opioids (IV fentanyl and/or hydromorphone), given as needed throughout the intraoperative period, per usual practice at practitioner's discretion. Patients in the long-duration opioid group receive IV methadone HCl at 0.1mg/kg. These subjects receive methadone as their only intraoperative opioid, given as a single bolus at anesthetic induction. If needed, a second cohort will receive or 0.15mg/kg of age-based ideal body weight. Following extubation, patients may receive incremental doses of

0.1mg/kg up to a maximum of 0.5mg/kg of dexmedetomidine (dosed at age-based ideal body weight) for sedation if needed, contingent upon adequate ventilatory rate.

For analgesia in the Post-Anesthesia Care Unit (PACU), patients in both groups may receive typical short-duration opioids (fentanyl or hydromorphone) as per usual routine care. It is not necessary that patients receive the same opioid postoperatively as intraoperatively. Post-op opioids orders are written by the pediatric anesthesiologist and opioids are given by PACU nurses per standard practice, based on developmentally appropriate pain scales (FLACC, Wong-Baker Faces, VAS) and institutional practice.

Pain scores via developmentally appropriate and validated pediatric pain scales will be confirmed by a blinded research coordinator OR a blinded secondary pediatric PACU nurse and charted in the EMR prior to administration of opioid analgesics. Adverse events will be recorded by a research coordinator who is blinded to randomization allocation and include: Respiratory depression (respiratory rate <10/min), reintubation, decreased oxygen saturation <85% for 30 seconds, excessive sedation (Pasero Opioid-induced Sedation Scale (POSS) score 3>1 hour, 4>15 minutes), unexpected PICU admission, and vomiting in PACU.

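### Does giving anesthesia providers the drug assignment undermine the claim of full double-blinding enough to require a change?

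*Combined protocol and SAP*

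**What the plan says.** Design & Procedures describes the trial as "Single center, randomized, double blind, parallel-group dose escalation investigation". Study Interventions says who is masked: "To ensure full double-blinding, subjects, investigators, and study team members evaluating patients will be blinded to drug treatment". The sentence just before that one says who is not: "Anesthesia providers receive a sealed envelope or email with Group (drug) assignment, group-specific instructions, and are advised on study procedures".

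Design & Procedures also shows that the two regimens look different to whoever gives them. For methadone, "These subjects receive methadone as their only intraoperative opioid, given as a single bolus at anesthetic induction". Control opioids are "given as needed throughout the intraoperative period".

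On recovery-room analgesia the same section says "Post-op opioids orders are written by the pediatric anesthesiologist and opioids are given by PACU nurses per standard practice". It adds that this dosing is to be "based on developmentally appropriate pain scales (FLACC, Wong-Baker Faces, VAS) and institutional practice". Before an opioid is given, the pain score is to be "confirmed by a blinded research coordinator OR a blinded secondary pediatric PACU nurse". A blinded coordinator records adverse events. Unblinding Procedures keeps the study team blinded while primary and secondary endpoint data are collected, apart from the interim analysis.

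The document does not state the blinding status of the person who writes the PACU opioid orders or of the nurse who gives the drug.

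**The concern.** The word *full* sits next to a sentence that hands the allocation to anesthesia providers, and a member of that specialty then writes the PACU orders. If the same person does both, someone who knows the child has had a long-acting opioid sets the terms on which further opioid is given. Opioid use is an outcome that clinicians partly determine, so blinded recording of the dose does not undo bias in how the dose was ordered.

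Two results could be touched. Non-methadone PACU opioid use feeds the escalation decision after the first cohort (Design & Procedures). It may also form part of the primary outcome, total OME/kg, whose time window is not stated (Data Analysis & Statistical Considerations). Lower ordering for methadone children would then be read as opioid sparing.

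**Working it through.** **Who knows what, role by role**

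| Role | Status in the document | Section |
|---|---|---|
| Subjects, investigators, evaluating team members | blinded | Study Interventions |
| Anesthesia provider giving the study opioid | receives the assignment | Study Interventions |
| Person confirming the pain score before dosing | blinded | Design & Procedures |
| Coordinator recording adverse events | blinded | Design & Procedures |
| Study team collecting endpoints | blinded, except for the interim analysis | Unblinding Procedures |
| PACU order writer | not stated | – |
| PACU nurse giving the opioid | not stated | – |

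No row contradicts another. The list of blinded roles omits the anesthesia provider, which fits that provider holding the assignment. Two rows are blank. No text says that the order writer is the person who received the envelope or email. The emergency-unblinding rule, which lets treating physicians call for the allocation, implies that at least some of them do not have it.

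**The plan's own power figures**

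Inputs from the power calculation: SD 0.3; interim 20 vs 10, difference 0.3, alpha 0.10; final 20 vs 20, difference 0.31, alpha 0.025. For a two-sided equal-variance t-test, the noncentrality is difference / (SD × √(1/n₁ + 1/n₂)), with n₁ + n₂ − 2 degrees of freedom.

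- Interim: 0.3 / (0.3 × √(1/20 + 1/10)) = 2.582, df 28, critical value 1.701. Power is 80.9%, against 80% stated.
- Final: 0.31 / (0.3 × √(1/20 + 1/20)) = 3.268, df 38, critical value 2.334. Power is 82.0%, against 82% stated.

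Both reproduce, so the same calculation can be used below.

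**What an ordering bias could do**

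Assume no true drug effect and a shift s in mean OME caused only by knowledge of the arm. The values of s are assumptions with no source in the document. The SD of 0.3 is given for total OME and is borrowed here for PACU use. Put s in place of the difference:

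| s | Interim noncentrality | Interim significant (nominal 10%) | Final noncentrality | Each final test significant (nominal 2.5%) |
|---|---|---|---|---|
| 0.02 | 0.172 | 10.5% | 0.211 | 2.8% |
| 0.05 | 0.430 | 13.0% | 0.527 | 4.5% |
| 0.10 | 0.861 | 21.7% | 1.054 | 11.1% |

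Over SD 0.2 to 0.5 with the same shifts, the interim rate runs from 10.2% to 35.2% and the final rate from 2.6% to 23.8%.

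Three limits apply to these rates.

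- The final figures need the whole shift to fall inside an outcome window that is not stated.
- The rates are two-sided, whereas the feared error is one-sided. At s = 0.02 and SD 0.3, the 10.5% splits into 7.0% favoring methadone (nominal 5%) and 3.5% favoring control.
- The effect of a false difference on escalation has no single direction. Design & Procedures escalates when PACU opioid use does not differ, and Data Analysis & Statistical Considerations escalates when methadone shows a significant effect. A false difference would block escalation under the first rule and prompt it under the second. That inconsistency is a separate matter.

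**What a change would buy**

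The natural remedy has two parts. The first restates blinding by role, which mostly repeats Study Interventions and fills the two blank rows. The second records, for each child, whether the order writer knew the arm and whether orders changed after the allocation was known. That record is self-report from the person whose conduct is in question. If orders are first written after allocation, a field on changed orders would read no for every child and miss the bias. Neither part alters an order, a dose, a test or a result.

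**The case for a change.** The strongest case for a change is that the safeguards protect the pain score but not the order. A blinded check that a child scores in a given range does not neutralize an order written more sparingly by someone who knows the arm. The check by a secondary nurse also leaves the primary nurse's status open. No text describes masking of the drug, and the regimens differ visibly. An unblinded intraoperative provider may be a reasonable design, but calling it full blinding is not accurate, and one sentence would put it right.

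Much of this stands as description. The word *full* claims more than the listed roles support, two roles are unstated, and blinded scoring does not reach the order itself.

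It does not stand that readers are misled, because the sentence next to the claim says the providers are told the drug. Nor does it stand that a bias has been shown: the path needs the order writer to know the arm and to order differently because of it, and the document establishes neither. That the principal investigator is a pediatric anesthesiologist adds nothing, since the plan does not say that investigators anesthetize subjects.

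**Conclusion.** No change to the plan is needed. What remains is one overstated word and the unstated status of two roles, in a 60-child pilot that discloses its unblinded provider and places a blinded check of the pain score before each opioid dose. Giving the allocation to the clinician who administers the drug is a fair trade-off when the control opioids are titrated at that clinician's discretion. Authors can describe blinding by role when they report the trial, and can note there any limitation on the PACU opioid result.

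The document gives no size for the bias. Under the assumed shifts at SD 0.3, the consequence runs from almost nothing (10.5% against 10% at the interim, 2.8% against 2.5% at the end) to material (21.7% and 11.1%), and nothing in the plan says where in that range the trial would fall. The conclusion rests on two readings: that the list of blinded roles means what it says, and that the order writer's knowledge of the arm is an open question rather than an established fact. Evidence that order writers routinely know the arm would strengthen the caveat on the PACU result. The proposed wording and data fields would still record the problem without removing it.

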#### Risk/Benefit Assessment

Recruitment and Informed Consent: The study will be conducted under appropriate Duke University IRB protocol and consent form approvals. The study will be conducted under the supervision of the PI, who is a Board-Certified pediatric anesthesiologist ([name]) with collaboration from a Board-Certified Anesthesiologist ([name]) with decades of experience in the conduct of human volunteer studies. Potential subjects will be identified through IRB-approved review of the surgical schedule prior to their surgery, at which time they will be contacted and asked if they are interested in participating. An IRB-approved phone screen will be conducted. Subjects that wish to participate may sign paper consent on the day of surgery when allowing sufficient time for explanations, questions and answers. If interested and willing, subjects may also be fully consented using IRB approved eICF. Informed consent must be given and signed by parents and/or legal guardian. Children greater than or equal to 12 years of age must provide verbal assent to be in the study.

#### Protections against Risk:

- i) Eligibility criteria exclude patients with known renal or hepatic disease, which may affect opioid disposition, pregnant females, those with severe sleep apnea with apnea hypopnea index > 10 and those who require planned ICU admission post operatively.
- ii) Methadone dosing is fixed, using age based ideal body weight, rather than actual body weight, to obviate risk of excessive dosing due to obesity.
- iii) Dose escalation will only occur if there are no adverse events in the initial dosing group

- iv) If nausea and/or vomiting occur, patients will be treated using the standard of care for all post-anesthesia nausea and vomiting. Respiratory depression with a respiratory rate <10 breaths/minute or hypoxia with oxygen saturation less than 85% for > 30 seconds will be monitored closely. If treatment is required, naloxone will be used. Patients will be routinely monitored by pulse oximetry, and receive supplemental oxygen if dictated, according to standard anesthesia practice.
- v) Research subjects will receive pre-operative, intra-operative and post-operative routine monitoring by anesthesiology and nursing staff.
- vi) The risk of breach of protected health information will be minimized by limiting the number of people within the research group who have access to identified data which will be described in the data monitoring safety plan.

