### **Data Analysis & Statistical Considerations**

Descriptive statistics for each treatment group will be computed for patient demographic and characteristic variables. Since our randomization scheme will have balanced the age effect between treatment groups, we anticipate the demographic and patient characteristic variables will be balanced across groups. For the continuous outcome measures (primary and most of secondary outcomes), we will conduct two-sample t-test to test the outcome difference (e.g., total OME difference) between treatment groups. For categorical outcomes (e.g., PACU side effects and adverse events), chi-square or Fisher exact tests will be applied as appropriate. Considering this is a pilot study for dose finding, we will relax the significance threshold to 0.1 for the interim analysis. Using the primary outcome, total OME/kg as an example, a two-sample t-test will be performed for comparing total OME difference between 20 methadone (0.1mg/kg) treated patients to 10 controls based on significance threshold of 0.10. If methadone showed significant effect on the outcome measure, the higher dose arm (0.15 mg/kg age ideal body weight) will be pursued. In the final analysis, similarly, two-sample test

will be used to test the total OME difference between methadone and control groups for both dose levels. To correct for multiple testing, the significance threshold in the final analysis will be set at 0.025. If there are covariates showing significant difference between treatment groups, we will perform multivariable linear regression analysis to test the treatment effect after adjusting for one selected covariate and examine if the treatment effect remains the same as that found in the two-sample t-test. The reason to restrict to one covariate in the model was to avoid model overfitting considering there will be only 20 samples per group. Similar analysis strategy will be applied to other outcome measures.

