#### **Unblinding Procedures:**

Emergency Unblinding is appropriate in the unlikely situation of a medical emergency (as determined by the PI or treating physicians, APPs) where knowledge of the treatment allocation is likely to have a significant effect on the clinical management of the enrolled subject and would be instrumental in immediate treatment decisions. In an emergency, it may not be feasible to obtain prior approval from the PI. In this case, after the subject is successfully unblinded, there must be clear documentation explaining why unblinding was necessary. The PI, IRB, and Research Practice Manager will be notified as soon as possible.

Accidental Unblinding: If a subject is accidentally unblinded, clear documentation of events must be recorded, as well as communication with the PI and Research Practice Manager. The treatment assignment must not be revealed to any other members of the study staff, pharmacy staff, or to the subject, unless written approval from the study sponsor is obtained. Every effort should be made to maintain what remains of the blind. In this case, a protocol deviation should be reported to the IRB of record.

Interim Analysis: Patients will be unblinded for the interim analysis by a member of the Department of Biostatistics. The interim analysis will determine if a dose escalation is indicated. Once the partial analysis is complete, the study we resume either at the same dose of

methadone (0.1mg/kg age ideal body weight or an increased dose 0.15mg/kg age ideal body weight).

Primary and secondary endpoint data collection will occur while the study team is blinded with exception of the interim analysis. Once all patients have completed the all parts of the study, final unblinding will occur.

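### The safety condition for escalating methadone to 0.15 mg/kg is written two incompatible ways: no adverse events at 0.1 mg/kg, or no increase in adverse events

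*Combined protocol and SAP*

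**What the plan says.** Protections against Risk, item iii, makes a clean record in the first methadone cohort a requirement: "Dose escalation will only occur if there are no adverse events in the initial dosing group".

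Design & Procedures, in both paragraphs of the study design text, says escalation will occur given "no difference in non-methadone PACU opioid use and no increased adverse events". It names no comparator, count or threshold for the adverse-event part.

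Two other places deal with the same decision without a safety condition. Data Analysis & Statistical Considerations says: "If methadone showed significant effect on the outcome measure, the higher dose arm (0.15 mg/kg age ideal body weight) will be pursued". Unblinding Procedures says: "The interim analysis will determine if a dose escalation is indicated".

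On which events count, the care subsection of Design & Procedures lists respiratory depression, reintubation, desaturation, excessive sedation, "unexpected PICU admission, and vomiting in PACU". Specific aim 2 in Purpose of the Study hypothesises no greater incidence of adverse events with methadone, and names only respiratory depression and excessive sedation in brackets.

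The IND-exemption argument in Study Interventions relies on a "purposeful conservative dosage chosen for study with protective and specific dose escalation criteria".

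**The concern.** Item iii is a necessary condition (escalate only if). The Design & Procedures sentence is a sufficient one (escalate if). They cannot both be followed when at least one methadone child has an event, events are not increased, and the opioid condition is met.

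This is the only stated safety condition before children receive a higher dose of a long-acting opioid. The interim data will be unblinded, so a choice between the wordings made at that time would be post hoc. A pair of rules that can give opposite answers is also hard to describe as specific, which is the term used in the IND-exemption argument.

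**Working it through.** **1. The plan's own figures.** No operating figure is given for the safety condition. The power figures under Power calculation do reproduce with a two-sided equal-variance t-test (noncentral t):
- Interim, 20 vs 10, difference 0.3, SD 0.3, alpha 0.10: noncentrality 0.3/(0.3·√(1/20+1/10)) = 2.58, power 80.9% (stated 80%).
- Final, 20 vs 20, difference 0.31, SD 0.3, alpha 0.025: power 82.0% (stated 82%).

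The interim figure is used again in step 5.

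**2. The logical conflict, with no rates needed.** Take 1/20 methadone (5%) and 1/10 control (10%). Events are not increased, so Design & Procedures directs escalation if the opioid condition holds. Item iii forbids it. Under a numerical comparison the conflict runs one way: zero methadone events can never exceed the control rate, so item iii never permits what the safety clause in Design & Procedures forbids.

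**3. How lax the comparative wording could be.** The statistics section assigns chi-square or Fisher tests to adverse events and sets the interim threshold at 0.10. It does not tie these to the escalation decision, but reading not increased as not significantly increased is plausible. With 0/10 control events, two-sided Fisher gives p = 0.14 at 5/20 and p = 0.074 at 6/20. Five methadone events against none would pass; six is the first count to block.

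**4. How often the safety clause passes.** Group sizes are from Design & Procedures: "we will randomly assign 20 patients to methadone 0.1 mg/kg and 10 patients to typical shortduration opioid (controls"). Event rates are assumptions. Let a ~ Bin(20, p1) for methadone and b ~ Bin(10, p2) for control, enumerated exactly.
- Zero events: P(a = 0) = (1 − p1)^20.
- Numerical: P(a/20 ≤ b/10).
- Fisher: P(no two-sided p < 0.10 in the harmful direction).
- Clauses disagree (numerical reading): P(a ≥ 1 and a/20 ≤ b/10).

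| Assumed risk, methadone vs control | Zero in 20 | Numerical | Fisher | Clauses disagree (numerical) |
|---|---|---|---|---|
| 1% vs 1% | 82% | 84% | ~100% | 1.7% |
| 5% vs 5% | 36% | 59% | >99.9% | 23% |
| 10% vs 10% | 12% | 56% | 99.6% | 44% |
| 20% vs 5% | 1% | 13% | 88% | 12% |

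As a check at 5%: 0.95^20 = 0.358, and 0.592 − 0.358 = 0.234 up to rounding, the disagreement figure.

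**5. From clause disagreement to opposite instructions.** Design & Procedures directs escalation only if its opioid condition also holds. Assume that condition is the interim t-test of step 1 and is independent of adverse events. At the planned effect, no difference is found in 1 − 0.809 = 19% of trials; with no opioid effect, in 90%.
- 5% risk: 0.233 × 0.19 = 4%; 0.233 × 0.90 = 21%.
- 10% risk: 0.439 × 0.19 = 8%; 0.439 × 0.90 = 39%.

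**The case against.** The strongest reply is that item iii is loose shorthand for no increase, and that the documents point to a comparison: aim 2 speaks of no greater incidence, and the statistics section supplies tests for adverse events. This stands in part, since the documents are not silent on how to compare. It does not remove the conflict, because item iii does not say this, and the test-based reading it supports is the most permissive one.

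A second reply is that the stakes are bounded. The step to 0.15 mg/kg is single and lies inside the 0.1–0.3 mg/kg range that the protocol cites, with monitoring and naloxone available. Treating item iii as binding is a conservative default. At equal risk its cost is a lost escalation, not harm. This stands, and it lowers the severity.

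Three stronger readings are tempting and not supported.
- A reader might take 23% or 44% as the chance that the trial receives opposite instructions. Those figures cover the safety clauses alone and are upper bounds.
- A reader might take the statistics section as a rival rule that dispenses with safety. It omits the condition; it does not cancel it.
- A reader might infer from item iv, "If nausea and/or vomiting occur, patients will be treated using the standard of care for all post-anesthesia nausea and vomiting", that vomiting does not count towards escalation. That sentence describes management, and the same item also covers respiratory depression and hypoxia. The real inconsistency in scope is between the recorded-event list, which includes vomiting in PACU, and aim 2, which names two events only.

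**Conclusion.** The safety condition is contradictory as written, and no section resolves it. That conclusion rests on the text alone. Its practical size rests on assumed event rates: little separates zero-in-20 from a numerical comparison at 1% (82% vs 84%), while at 10% the clause passes in 12%, 56% or 99.6% of trials according to the reading. Opposite escalation instructions, under the assumptions in step 5, would arise in about 4% to 21% of trials at a 5% rate and 8% to 39% at 10%.

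A reader might infer that the plan would readily expose children to a harmful dose. The documents do not support that in general: at 20% vs 5% risk, zero-in-20 passes in 1% of trials and the numerical comparison in 13%. The exception is a non-significant test used as the gate, which would pass 88%. This should be fixed, but it is not a critical flaw. The separate mismatch over the opioid-use trigger (no difference in one section, a significant effect in another) is outside this point.

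**What to change.** Before the unblinded interim analysis, replace the wording in Design & Procedures (both places) and in item iii, and add to the escalation sentence in the statistics section, one identical condition, applied in addition to the efficacy rule. For example: escalation additionally requires that no more than k of the 20 methadone 0.1 mg/kg subjects had any of the following events, followed by the list.

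- Draw the list from the events already recorded, with at least respiratory depression and excessive sedation, and say whether PACU vomiting counts.
- Fix k in advance. k = 0 keeps the protection that item iii now states; the value is the sponsor's choice.
- State that a non-significant test on 20 vs 10 does not serve as the gate.

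The cost is a wording amendment in three sections, with no extra patients or data. The trade-off is that a strict limit can stop escalation when methadone adds no risk. At a 5% event rate, k = 0 stops 64% of trials (1 − 0.358) and k = 1 stops 26% (1 − 0.736); at 10% these become 88% and 61%.
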